7.3. Screening and Diagnosis

Potential subjects will be pre-identified by the site because of confirmed or suspected PCDH19 genetic mutation testing as part of their standard of care epilepsy work-up. Potential subjects will have historical seizure diary charting 12 weeks prior to screening. Eligible historical seizure diaries will need to include daily logs of seizure types and frequency and denote the absence of seizures on those days where no seizures occurred.

7.3.1. Informed Consent / Assent

Procedures specific to this protocol and not otherwise considered standard of care, will not be performed until written informed consent/Assent from the subject/parent/caregiver/LAR has been appropriately obtained.

7.3.2. Drug Screen

A drug screen (plasma) will be performed to test for THC and non-approved CBD during the DB phase at Visit 1 (screening), Visit 2 (baseline/randomization), and Visit 5 (final DB/first OL visit). If the screening drug test is positive at Visit 1 (screening), a confirmatory retest, via plasma, will be performed after 2 weeks. A drug screen may be performed at any time at Investigator's discretion. A positive drug test during the DB phase will result in early termination.

7.3.3. Demographics and Medical History

Demographics including age, gender, ethnicity and race will be collected. In addition to the genetic confirmation of pathogenic or likely pathogenic *PCDH19* variant, relevant medical history, including but not limited to the age of seizure onset, other physical disabilities such as scoliosis, visual impairment, sensory problems and gastrointestinal difficulties will also be assessed; the subject's developmental history will also be assessed. Demographics and Medical History will be reviewed and collected at the Visit 1 (screening). A review of the subject's Medical History will be performed again at Visit 2 (baseline/randomization).

7.3.4. Historical Seizure Calendar Review

It is very common for parent/caregivers/LARs to maintain daily seizure calendars for this subject population, which capture both seizure type and frequency. A 12-week historical seizure calendar will be reviewed at the screening visit to determine eligibility per inclusion/exclusion criteria. Acceptable historical seizure calendars will need to denote both seizure type and frequency and days that no seizures occur.

In the event the subject is not able to provide eligible historical seizure diary (at least 12 weeks prior to screening), the informed consent/assent will need to be obtained and the parent/caregiver will need to chart prospectively.

7.3.5. Genetic Testing

Molecular confirmation of a pathogenic or likely pathogenic *PCDH19* mutation is required. Genetic mutations will be confirmed by the sponsor's chosen central laboratory. The PI must review the results of the genetic analysis and confirm that the causal relationship to the epilepsy syndrome is likely. If the subject has a de novo *PCDH19* VUS then the central assessor, PI, and Sponsor will review study inclusion. Some subjects may have multiple *PCDH19* mutations that include both VUS and pathogenic variants. In these cases, the subject is known to have a pathogenic variant and is eligible (does not require discussion with expert).

In the event that parents/caregivers/LAR do not have genetic testing results with a confirmed PCDH19-related epilepsy diagnosis per standard of care, written informed consent/assent will be obtained.

Instructions for genetic testing sample collection and processing can be found in the central laboratory manual.

7.3.6. Seizure Identification and Diagnostic Review

Per the inclusion criteria, enrollment into the study will be based on the presence and frequency of all countable focal seizures that include progressive hypotonia and impaired awareness, or any countable focal or generalized seizure with a clear motor component.

To standardize seizure identification and classification in the study, a SIF/DRF will be submitted and reviewed by the Epilepsy Study Consortium. Approval of the SIF/DRF will be required prior to randomization. In addition to this form, videos of the subject's seizure types will also be reviewed to confirm proper classification provided that the parent/caregiver is able to capture video of these seizure types, parents/caregivers are able to provide videos to the site for upload onto a secure encrypted server in a manner consistent with ICH/GCP and if local IRB/EC regulations grants approval for collection of such videos. Parents/caregivers must make every effort to capture 1 example of each of the primary seizure types that their child experiences. Although it is acknowledged that some seizure types (e.g., atonic/drop seizures) may be more difficult to capture on video, this information will provide valuable verification of this seizure type and the attempt should be made.

Instructions for completion of the SIF/DRF and submission of videos can be found in the Investigator Site File.

7.4. Efficacy Assessments

Efficacy as determined by a reduction in seizures will be evaluated by collecting daily seizure type and frequency in an electronic seizure diary.

7.4.1. Seizure Type and Frequency

Parent/caregiver/LAR will record daily seizure frequency denoting seizure type and frequency in an electronic seizure diary (eDiary). In rare cases when an eDiary completion is not feasible, a paper diary will be used to log daily seizure type and frequency. These cases will need approval by the sponsor. Primary seizure types of countable focal seizures that include progressive hypotonia and impaired awareness, or any countable focal or generalized seizure with a clear motor component, will be counted towards the primary endpoint.

[figure not shown]
Subjects or parent/caregiver/LAR are to record administration of IP and background AEDs in the eDiary/seizure calendar. Compliance with IP treatment will be assessed by inspecting the subjects' eDiary/seizure calendar and returned supplies with queries as necessary. As a generally accepted guideline, subjects should remain 80% compliant with diary entries. Parents/caregivers who fall short of this standard will be re-educated on the importance of adhering to daily seizure, IP and non-study AED recording and a deviation recorded.

For recording of seizures in the eDiary, seizure events will be recorded either as a countable seizure or a series of continuous uncountable seizures. Both of these events will be counted as 1 seizure (equally weighted) in the efficacy analysis.

A seizure cluster will be defined as 3 or more seizure events (either a countable or a series of continuous uncountable seizures), occurring within a period of time, followed by a period of at least 24 hours of seizure-freedom. For example (Figure 2):

1. If a child experiences 3 seizure events at 5:00, 5:30, and 6:00 PM on Monday, and the next seizure event occurs before 6:00 PM on Tuesday, the Monday and Tuesday seizure events are considered part of the same seizure cluster (Figure 2, Scenario 1).
2. If a child experiences 3 seizure events at 5:00, 5:30, and 6:00 PM on Monday, and the next seizure event occurs at 6:00 PM or later on Tuesday, the Tuesday seizure event is not considered part of the same cluster (Figure 2, Scenario 2).

Figure 2: Seizure Cluster Designation Examples

7.4.2. Rescue Medication

The type, dose, date, and frequency of rescue medication will be recorded in the eDiary and reviewed every visit.

7.4.3. Children's Sleep Habits Questionnaire (CSHQ)

The Children's Sleep Habits Questionnaire (CSHQ) is a psychological questionnaire designed to measure sleep behaviors in children and adolescents. The 33-question test is filled out by the parent/caregiver/LAR.

CSHQ will be assessed as follows: in the DB phase at Visit 2 (baseline/randomization) and Visit 5 (Week 17; also Final DB Visit/First OL Visit in OL phase); in the OL phase at Visit 7 (Week 36) and Visit 9 (Week 68) and thereafter every 16 weeks for the duration of this phase; and at the Final OL Visit.

7.4.4. Behavior Rating Inventory of Executive Function (BRIEF, Preschool Version BRIEF-P)

[figure not shown]
The Behavior Rating Inventory of Executive Function (BRIEF) is an 86-item questionnaire designed to assess executive function behaviors in the school and home environments in individuals 5-18 years of age. The preschool version (BRIEF-P) is a 63-item modified form and is typically utilized in individuals 2-5 years of age. For this study, the BRIEF-P will be used for any subject less than 5 years of age. The questionnaire is completed by the parents/caregiver/LAR.

BRIEF (BRIEF-P where appropriate) will be assessed as follows: in the DB phase at Visit 2 (baseline/randomization) and Visit 5 (Week 17; also Final DB Visit/First OL Visit in OL phase); in the OL phase at Visit 7 (Week 36) and Visit 9 (Week 68) and thereafter every 16 weeks for the duration of this phase; and at the Final OL Visit.

7.4.5. Aberrant Behavior Checklist – Community (ABC-C)

The ABC-C is a questionnaire designed to assess problematic behavior at home, in educational and work setting, and in residential and community-based facilities.

The ABC-C will be assessed as follows: in the DB phase at Visit 2 (baseline/randomization) and Visit 5 (Week 17; also Final DB Visit/First OL Visit in OL phase); in the OL phase at Visit 7 (Week 36) and Visit 9 (Week 68) and thereafter every 16 weeks for the duration of this phase; and at the Final OL Visit.

7.6. Safety Assessments

Safety will be evaluated by collecting the assessments detailed in the sections below.

Baseline is defined as the last non-missing value obtained before the first DB treatment. If any of the baseline safety assessments are outside of normal limits, and the investigator feels is medically significant, the subject may not be randomized. Assessments performed at multiple post-baseline time points will be summarized at each time point for which they are scheduled, but the listings will also include any assessments performed at unscheduled time points.

7.6.1. Adverse Events

Details regarding AEs and SAEs are provided in Section 8.

7.6.2. Vital Signs

Vital signs including HR (bpm), RR (breaths/minute), body temperature (C/F), BP (mmHg), and weight will be collected at every clinic visit starting with Visit 1 other than the Safety Follow-Up Visit. Height will be collected at Visit 1 (screening) (during DB phase) and during the OL phase at Visit 7 (Week 36), at Visit 8 (Week 52), annually thereafter (except for the Safety Follow-up Visit), and at the Final OL Visit.

7.6.3. Physical/Neurological/Developmental Examinations

The full physical examination will include the following systems:

- General appearance
- Head (eyes, ears, nose and throat)
- Cardiovascular
- Respiratory
- Gastrointestinal
- Genitourinary
- Musculoskeletal
- Endocrine/Metabolic
- Hematologic/lymphatic
- Skin
- Other systems as appropriate

The full neurological examination will include:

- Cranial nerves
- Motor exam
- Sensory exam

- Reflexes
- Coordination/Cerebellar

The full developmental examination will include:

- Speech/language
 - Makes identifiable sounds for specific objects/people
 - Repeats sounds
 - Single words
 - Multiple words
 - Makes a sentence
 - Replies to question in an identifiable sound, single word, multiple word, sentence
 - Other abilities
- Motor
 - Sits with support
 - Sits independently
 - Crawls
 - Stands with support
 - Stands independently
 - Takes steps with assistance
 - Walks independently
 - Other abilities
- Social
 - Smiles appropriately to situation
 - Makes eye contact

Follow up physical, neurological, and developmental examinations are abbreviated examinations that ask whether there have been clinically significant changes or new abnormalities in the subject's physical, neurological, and developmental examinations since the last full examination.

7.6.4. ECG

Electrocardiograms will be performed to collect the electrical activity of the heart throughout the study to monitor safety. An evaluation of normal by a physician must be obtained before the subject is randomized to the DB phase.

ECGs will be performed as follows:

- DB phase:
 - Visit 2 (baseline/randomization)
 - Visit 3 (Week 5)
 - Visit 5 (Week 17 = Final DB Visit/First OL phase visit)

- OL phase:
 - Visit 6 (Week 21)
 - Visit 8 (Week 52 and then yearly)
 - Final OL Visit

7.6.5. Clinical Laboratory Tests

Clinical laboratory tests are listed in Section 12.2 and will be collected per the schedules listed in Table 1 and Table 2. If any test result is unexpectedly out of range, a repeat test can be performed at any time as decided by the PI to confirm the initial result.

The following liver function and eGFR tests will be monitored throughout the study as follows.

- If AST or ALT increases > 3 times ULN during the study, subject should be followed with weekly laboratory repeat testing and continue in study if levels trending down. Subject will be discontinued if levels do not decline to under $3 \times$ ULN.
- If total bilirubin increases to $1.5 \times$ ULN or more during study, the subject will be discontinued.
- Subjects with significant renal insufficiency, eGFR < 30 mL/min (calculated using the Cockcroft-Gault formula), will be discontinued if the criterion is met post baseline.

If any of the criteria above are deemed clinically significant by the PI, then the sponsor's medical monitor should be contacted.

Due to the difficulty in obtaining urine samples, urinalysis will be conducted as follows: during the DB phase at Visit 1 (screening) or baseline/randomization (Visit 2), Visit 3, and at Week 17 (Visit 5; also Final DB Visit/First OL Visit in OL phase); in the OL phase at Visit 7 (Week 36), Visit 8 (Week 52) and annually thereafter, or at the Safety Follow-up Post-Taper visit if IP is discontinued; and at the Final OL Visit. An attempt will be made to collect a urine sample at screening to perform the study-related urinalysis. Otherwise, the urine sample for the urinalysis can be collected at baseline.

7.6.6. Tanner Staging

The Tanner scale (also known as the Tanner stages) is a scale of physical development in children, adolescents, and adults. The scale defines physical measurements of development based on external primary and secondary sex characteristics. Subjects will be evaluated and rated as Tanner I, Tanner II, Tanner III, Tanner IV, and Tanner V. Tanner staging will occur during the DB phase at Visit 1 (screening); during the OL phase at Visit 8 (Week 52) and thereafter assessed annually for the duration of the subject's participation in this phase; and at the Final OL Visit.

7.6.7. Investigational Product PK

Please refer to Section 7.7 for additional details regarding Pharmacokinetic Assessments.

7.6.8. Concomitant AED levels

Concomitant AED levels are not mandatory but will be collected per sites' standard of care. If AED levels are considered SOC, they will be assessed as follows: during the DB phase at Visit 1 (screening), Visit 2 (baseline/randomization), Visit 3 (Week 5), Visit 4 (Week 9), and Visit 5 (Week 17; also Final DB Visit/First OL Visit in OL phase); in the OL phase of the study at the timepoints noted in Table 1 and Table 2; at the Final OL Visit; and at the Safety Follow-Up Post-Taper Visit. The results, date, and time of last AED dose and date and time of AED PK sample will be recorded in the eCRF.

7.6.9. Adverse Events

Details regarding AEs and SAEs are provided in Section 8.

7.7. Pharmacokinetic Assessments

A population PK approach addressing the relationship between GNX PK parameters and individual characteristics will be implemented during the study.

Blood sampling for PK evaluation must be performed at the protocol-scheduled times within the windows specified in Table 1 and Table 2. Exact time of sample withdrawal and drug intake will be recorded in the electronic case report form (eCRF). One blood sample will be obtained at the following visits for PK analyses:

During the DB Phase:

- Visit 3 (Week 5): between 1 and 5 hours since the last investigational product dosing
- Visit 4 (Week 9): between 4 and 8 hours since the last investigational product dosing

During the OL Phase:

- Visit 6 (Week 21): between 1 and 5 hours since the last investigational product dosing
- Visit 8 (Week 52): between 1 and 5 hours since the last investigational product dosing

For all other PK draws, there is no specified time to draw the PK sample and can be drawn when convenient during the study visit for Visit 5 (Week 17), Visit 7 (Week 36), Visit 9 (Week 68), and every 16 weeks for the duration of the open-label phase.

Exact time of sample withdrawal and drug intake will be recorded in the electronic case report form (eCRF).

8. ADVERSE AND SERIOUS ADVERSE EVENT ASSESSMENTS

8.1. Definition of Adverse Events, Period of Observation, Recording of Adverse Events

An AE is any untoward medical occurrence in a clinical investigation subject who has been administered a pharmaceutical product; it does not necessarily have a causal relationship with this treatment. An AE can therefore be any unfavorable and unintended sign (including an abnormal laboratory finding), symptom, or disease temporally associated with the use of a medicinal (investigational) product, whether or not related to the medicinal (investigational) product (International Conference on Harmonisation [ICH] Guidance E2A March 1995).

All AEs are collected from the time the informed consent (and subject assent) is signed until the defined follow-up period. This includes events occurring during the screening phase of the study, regardless of whether or not the IP has been administered. All AEs reported after the initiation of IP will be considered treatment-emergent AEs. Where possible, a diagnosis rather than a list of symptoms should be recorded. If a diagnosis has not been made, then each symptom should be listed individually. All AEs should be captured on the appropriate AE pages in the eCRF and in source documents. In addition to untoward AEs, unexpected benefits outside the IP indication should also be captured on the AE eCRF page.

All AEs must be followed to closure (the subject's health has returned to baseline status or all variables have returned to normal), regardless of whether the subject is still participating in the study. Closure indicates that an outcome is reached, stabilization is achieved (the PI does not expect any further improvement or worsening of the event), or the event is otherwise explained. When appropriate, medical tests and examinations are performed so that resolution of event(s) can be documented.

8.1.1. Severity Categorization

The severity of AEs must be recorded during the course of the event, including the start and stop dates for each change in severity. An event that changes in severity should be captured as a new event. Worsening of pretreatment events, after initiation of the IP, must be recorded as new AEs (eg, if a subject experiences mild intermittent dyspepsia prior to dosing of the IP, but the dyspepsia becomes severe and more frequent after the first dose of the IP has been administered, a new AE of severe dyspepsia [with the appropriate date of onset] is recorded on the appropriate eCRF page).

The medical assessment of severity is determined by using the following definitions:

Mild: A type of AE that is usually transient and may require only minimal treatment or therapeutic intervention. The event does not generally interfere with usual activities of daily living.

Moderate: A type of AE that is usually alleviated with specific therapeutic intervention. The event interferes with usual activities of daily living, causing discomfort, but poses no significant or permanent risk of harm to the research subject.

Severe: A type of AE that interrupts usual activities of daily living, that significantly affects clinical status, or that may require intensive therapeutic intervention.

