9.1 ADVERSE EVENTS

AEs will be coded by System Organ Class (SOC) and Preferred Term (PT) using MedDRA®, version 22.0 or higher. The verbatim term will be included in the AE listings. Except where indicated, the summary tables will include only treatment-emergent adverse events (TEAEs). All AEs, treatment-emergent or otherwise, will be

presented in subject data listings.

A TEAE is defined as an AE that starts or worsens on or after the first dosing day of study drug. The AE analyses for the DB treatment phase of the study will include AEs that start or worsen during that phase and will not include AEs that start or worsen during the OL phase; i.e., they will not include any AEs starting or worsening on or after the first dosing day of the OL phase.

For the OL phase of the study, the adverse event results will be summarized over just the OL phase as well as over the entire study (DB and OL phases) but the classification by the DB treatment applies only for the OL phase summary. The summarization over the entire study will include only subjects who were in the GNX group during the DB phase, regardless of whether they entered the OL, and all the subjects from the OL phase; i.e., it will include only the TEAEs following GNX exposure. The summarizations over just the OL phase will include TEAEs that occur or worsen on or after the first day of the OL phase; the summarizations over the entire study will include TEAEs that start or worsen on or after the first dosing day of GNX.

The TEAEs will be summarized as the number of events and the number and percentage of subjects with TEAEs. Subjects who report the same PT on multiple occasions will be counted once for the PT: under the highest severity (severe > moderate > mild) when summarized by severity and under the closest relationship (related > not related) to study drug when summarized by relationship.

If a subject reports multiple PTs for a SOC, the subject will be counted only once for that SOC. For the counting of events, all the PTs will be included in the counts, even when subjects have multiple PTs.

Non-treatment emergent AEs will only be listed.

TEAEs will be summarized as follows:

- An overview table of TEAEs, including number of events and number (%) of subjects with:
 - TEAEs
 - Serious AEs (SAEs)
 - Study drug related TEAEs
 - TEAEs by severity
 - TEAEs leading to study discontinuation
 - TEAEs leading to death
 - Adverse events of special interest (AESI)
- TEAEs by SOC and PT

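### A fall in AE severity opens a new record that SAP 9.1 can count as a further TEAE, inflating event counts and carrying double-blind events into the open-label and GNX-exposure tables

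*Protocol*

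**What the plan says.** **Collection.** Protocol 8.1.1 requires severity to be recorded "including the start and stop dates for each change in severity", and then states: "An event that changes in severity should be captured as a new event". The next sentence deals with events present before treatment: "Worsening of pretreatment events, after initiation of the IP, must be recorded as new AEs". Protocol 8.1 has AEs collected from consent onward, so the baseline period is covered.

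**Classification.** SAP 9.1: "A TEAE is defined as an AE that starts or worsens on or after the first dosing day of study drug". The same onset-or-worsening test is applied from the first open-label day for the open-label tables. It is applied from the first GNX dose for the whole-study summary, which is meant to hold only TEAEs that follow GNX exposure. Table 3 of that section imputes missing start dates in order to decide treatment emergence. Protocol 8.1 words the test differently: "All AEs reported after the initiation of IP will be considered treatment-emergent AEs".

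**Counting.** SAP 9.1: "The TEAEs will be summarized as the number of events and the number and percentage of subjects with TEAEs". At subject level, "Subjects who report the same PT on multiple occasions will be counted once for the PT", at the highest severity when tabulated by severity. At event level, "For the counting of events, all the PTs will be included in the counts, even when subjects have multiple PTs". Neither document joins consecutive severity records of one episode, and neither sets aside a record that exists only because severity fell.

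**The concern.** The word worsens in the SAP definition shows that treatment emergence is meant to capture onset or deterioration. The collection rule works against that. When an event eases and the site opens a new record, the record has a start date of its own and meets the starts limb of the definition, although nothing began or got worse.

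Two outputs are exposed. First, the event-count columns, including the overview table's rows for all TEAEs, drug-related TEAEs and severity. Second, the tables that open at a later date. An event with onset in the double-blind phase that is still resolving when open-label dosing starts can reappear as new harm. If the subject was on placebo, an event that began without any GNX exposure can be reported as following GNX exposure.

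**Working it through.** The plan states no figure on this point, so there is nothing to reproduce. The check applies the written rules to hypothetical AE courses.

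**Inputs.** One record per severity level passed through, each with its own start date (Protocol 8.1.1). A record counts in a table if it starts on or after the relevant first dose (SAP 9.1). Every such record adds to the event count. A subject adds at most 1 per preferred term (SAP 9.1).

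**Formula.** Events as written = (1 if onset is on or after the relevant first dose, otherwise 0) + number of severity changes on or after that dose.

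- A. Mild, moderate, severe, moderate, mild, all double-blind: 1 + 4 = 5.
- B. Severe, moderate, mild, all double-blind: 1 + 2 = 3.
- C. Severe before dosing, then moderate and mild after dosing: 0 + 2 = 2.
- D. Moderate in the double-blind phase, mild after open-label start: double-blind 1 + 0 = 1; open-label 0 + 1 = 1.
- E. Course D in a placebo subject, in the whole-study GNX summary: 0 + 1 = 1.

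These are compared with a rule that counts only onset or worsening, and with the episode rule proposed below. Entries are events / subjects for that preferred term.

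| Course | As written | Onset or worsening only | Episode rule |
|---|---|---|---|
| A | 5 / 1 | 3 / 1 | 1 / 1 |
| B | 3 / 1 | 1 / 1 | 1 / 1 |
| C | 2 / 1 | 0 / 0 | 0 / 0 |
| D, double-blind table | 1 / 1 | 1 / 1 | 1 / 1 |
| D, open-label table | 1 / 1 | 0 / 0 | 0 / 0 |
| E, whole-study GNX summary | 1 / 1 | 0 / 0 | 0 / 0 |

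**Reading the table.** Each step down after dosing adds one event. In A and B, where onset and resolution fall in the same phase, the subject count is unchanged. In C, D and E the subject count also goes from 0 to 1, and the once-per-term rule cannot correct this because the right count is zero. C depends on how sites read Protocol 8.1.1 (see the objection); D and E do not.

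**The case against.** **Protocol 8.1.1 never mentions improvement.** True. The outcome category for a recovering event (Protocol 8.1.3) and follow-up to closure (Protocol 8.1) suggest that one record could carry an improving event. But the sentence covers any change in severity and the one before it asks for dates at each change, so a site following the text opens a new record.

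**Pretreatment events have their own sentence, which names worsening only.** This has force. If the general sentence already reopened them at every change, the specific one would add nothing. Course C therefore arises only if sites apply the general sentence to pretreatment events. A reader might infer a shift of about 8 percentage points in double-blind incidence. That is only 1 / 12.5, with 25 subjects split evenly. It is one subject in one preferred-term row, it rests on course C, and it is not an estimate of bias.

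**The SAP does not direct multiple counting of one episode.** Its event-count sentence concerns subjects with several preferred terms and is silent on several severity records of one term. But it offers no way to identify the underlying event, so the default is to count records. All AEs are listed, so reopened records could be traced, but not from the summary tables.

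**The extra records will fall on GNX.** A reader might infer this from somnolence, reported in 33.9% on GNX against 5.6% on placebo in the fragile X trial described in Protocol 1.2. It is plausible but unquantified. Somnolence appears in this protocol as a tolerability issue; the AEs of special interest in Protocol 8.3 are rash and reproductive or breast events.

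**The open-label carry-over touches no controlled comparison.** Correct, since all subjects then receive GNX. It still misstates what emerged on open-label treatment, and course E misattributes a placebo-onset event.

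**Protocol 8.1 adds a conflicting definition.** Its wording does differ from the SAP. However, Protocol 9.3 defers to the SAP for updated details, so aligning it is housekeeping.

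**Conclusion.** The point holds for event counts and for carry-over into later tables. As written, each post-dose fall in severity can add a TEAE: up to 3 events instead of 1 for a simple severe-to-mild resolution. A double-blind event improving after open-label start can add an event and a subject to the open-label table. If it began on placebo, it can add both to the GNX-exposure summary.

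The documents do not support the stronger reading that double-blind incidence percentages are generally inflated. For events with onset in that phase, counting each subject once per preferred term leaves them unchanged. The pre-dose route is open only on one reading of Protocol 8.1.1.

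The conclusion assumes that sites follow the general sentence of 8.1.1 for improvement as well as worsening, and that programming takes each record's start date at face value. The total effect and its balance between arms cannot be estimated, because no frequency of severity changes is given.

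**What to change.** Add one paragraph to SAP 9.1:

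- Consecutive records of the same preferred term in a subject, where the next starts on the stop date of the previous one or the day after, form one episode. Where dates are partial, apply this after the Table 3 imputation.
- An episode is counted as one event, at its maximum severity within the phase being tabulated.
- It is treatment-emergent, or open-label-emergent, only if its first record starts, or its severity increases, on or after the relevant first dose. For the whole-study summary that is the first GNX dose.
- A record opened because severity fell is not a TEAE.

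Also align the reporting-based sentence in Protocol 8.1 with the SAP definition.

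The cost is one paragraph and a programming rule on dates and severities already collected; site procedures do not change. The small downside is that true recurrences whose dates abut are merged.
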